## **1.0 Objectives\***

### *1.1 Purpose*

The purpose of this study is to perform a proof-of-concept trial for a novel phone-based positive psychology intervention for hematopoietic stem cell transplant (HSCT) patients to assess feasibility and acceptability of the intervention prior to a larger pilot study.

### *1.2 Specific Aims/Objectives*

**Specific Aim #1 (Feasibility and Acceptability; primary aim):** To assess whether the novel positive psychology intervention is feasible (participants will complete 5 out of 8 phone sessions) and acceptable in HSCT patients.

**Specific Aim #2 (Effects on psychological outcomes):** To assess whether this preliminary intervention appears to result in improvement in positive affect and other psychological well-being factors as measured by dispositional optimism, anxiety, and depression.

**Specific Aim #3 (Effects on other outcomes):** To examine the impact of the intervention on overall function and health-related quality of life.

### *1.3 Hypothesis*

**Hypothesis #1:** The PP exercises will be feasible (i.e., 5 of the 8 phone sessions will be completed by a majority of patients) and acceptable (mean score of at least 6 out of 10 on ratings of ease of completion and subjective utility of the exercises). Furthermore, we will obtain complete objective follow-up data in at least 80% of enrolled participants at the end of the intervention.

**Hypothesis #2:** The intervention will lead to improvements in positive affect and other psychological well-being factors as measured by dispositional optimism, anxiety, and depression at completion compared to baseline.

**Hypothesis #3:** The intervention will lead to improvements in health-related quality of life and functional outcomes at completion compared to baseline.

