**Weekly phone sessions for positive psychology intervention:** All participants will be asked to complete 8 weekly PP exercises and to speak with the interventionist weekly. Weekly phone sessions will last approximately 30 minutes. Prior to completing each phone session, participants will be asked to rate their current level of happiness and optimism, using a 10-point Likert scale. Immediately after completing the exercise and phone session, participants will rate the ease of exercise/session completion, overall utility of the exercise/phone session, and their current levels of happiness and optimism, all using 10-point Likert scales. These calls will be recorded so that a percentage (10%) of these recordings can be reviewed by research mentor, [name] to ensure that the PP intervention is being delivered as described in the protocol.

**Follow-up session:** The last week of the study will be used for a repeat of the self-assessment questionnaires obtained at the beginning of the study. This will be done either via phone or mail depending on patient preference.

**Positive Psychology Program Content.** All phone sessions will include (a) a review of the ease and utility of the week's PP exercise (b) a discussion of the

**PROTOCOL TITLE: Development of a positive psychology intervention to improve mood and health related quality of life in patients post hematopoietic stem cell transplantation- Proof of Concept Trial**

rationale of the next week's PP exercise through a guided review of the PP manual, and (c) assignment of the next week's PP exercise. During the calls, the interventionist and participant will also review the next section of the treatment manual and prepare for the upcoming week's exercise.

**Positive Psychology Exercises.** The PP exercises used in this study were selected based on the qualitative study results from the first phase of this study (IRB: 17-154), their superior performance in our pre-pilot research and others' work with medical populations. They will be grouped into three modules focusing on a different psychological state:

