**Follow-Up Session**

At the last week of the study, a member of the study staff will call participants to repeat the self-report questionnaires that were administered at baseline. Positive and Negative Affective Scale (PANAS) to measure positive affect, Life Orientation Test-Revised [LOT-R] to measure optimism and the Hospital Anxiety and Depression Scale [HADS] to measure anxiety and depression. We will also assess HSCT-specific HRQoL with the Functional Assessment of Cancer Therapy-Bone Marrow Transplantation [FACT-BMT] scale), fatigue (PROMIS-Fatigue-8a) and overall function (PROMIS-PF-20). Finally, patients will be asked about their experience in the study, including any aspects of the intervention or study procedures that could be improved. In sum, these scales should take approximately 30-40 minutes to complete. If participants would rather complete the follow-up questionnaires in written form rather than over the phone, we will send them a paper packet at the time of the follow-up.

Given the results of our prior PP studies in medical populations yielding a 64-85% completion rate of the exercises, and given that this is a feasibility study (i.e., we want to assess participants' willingness to complete the phone sessions), we will expect participants to complete at least 5 PP exercises. In other words, if a participant completes at least 5 sessions, missed sessions will not be considered a deviation from the protocol.

**Training.** The PP exercises for this trial have been identified via published literature, or directly from researchers, and modified appropriately for this population based on results from first phase of the study that the IRB approved (17-154). Additional text outlining the rationale and instructions for each exercise are in the written packets for each exercise that are provided to participants. [name] will engage in several training exercises prior to study initiation. [name] research mentor, [name], and his research group have had substantial experience in explaining and delivering PP exercises from their studies in cardiac and psychiatric patients, which will inform [name] training. Together with [name], [name] will review the treatment manual and the team's prior training manuals related to these exercises. They then will complete all exercises together to gain experience performing and reviewing each exercise.

*9.3 Procedures performed to lessen the probability or magnitude of risks.*

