**11.0 Data Management\* and Confidentiality**

*11.1 Data analysis plan, including any statistical procedures.*

Data will be downloaded from REDCap into the Stata statistical package. For Aims 1 and 2 (feasibility, acceptability, and immediate impact), descriptive statistics will be used to report proportion of phone session completion and mean scores on exercise ratings.

To compare mean scores on outcome variables for Aim 3, paired t tests will be used to explore mean differences between baseline and follow-up values. All statistical tests will be two-tailed and  $p < .05$  considered significant, though this study will not be powered to detect statistically significant differences between baseline and follow-up points. Given the sample size and potential for drop-out, we will also consider alternatives to a t-test such as non-parametric tests, effect size calculations to support feasibility of study assessment procedures.

*11.2 Power analysis.*

This exploratory proof-of-concept study with 25 patients (anticipated 10 patients to complete the study), as noted, will not be powered to detect statistically significant differences between baseline and follow-up points, and is designed to assess feasibility of methods.

*11.3 Data Security Plan.*

All source data (e.g., chart review data and participant self-report) will be entered into the REDCap database. The PI ([name]) will review this data to ensure that it is being entered correctly and will perform 'test downloads' of the data to ensure that it can be captured in the statistical package to be used in this study. We will also use

**PROTOCOL TITLE: Development of a positive psychology intervention to improve mood and health related quality of life in patients post hematopoietic stem cell transplantation- Proof of Concept Trial**

locked cabinets/offices and password-protected databases to store personal information. Only study staff (currently just the PI) will have any access to personally identifiable information about participants, and such access will be limited only to information necessary to complete study tasks.

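### Hypothesis 1 concludes that the exercises are feasible, but the plan counts only phone sessions and never the exercises done

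*Combined protocol and SAP*

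**What the plan says.** Aim 1 (section 1.2) defines the intervention as "feasible (participants will complete 5 out of 8 phone sessions". Hypothesis 1 (section 1.3) uses the same count but draws its conclusion about the exercises: "The PP exercises will be feasible (i.e., 5 of the 8 phone sessions will be completed by a majority of patients". It adds an acceptability criterion, a mean of at least 6 out of 10 on ease and utility of the exercises.

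Section 9.2 (weekly phone sessions) describes two tasks: "All participants will be asked to complete 8 weekly PP exercises and to speak with the interventionist weekly". The first exercise is handed out at the pre-intervention visit, before the first call. Each call then reviews the past week's exercise and assigns the next.

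The only rationale for the number 5 is under Follow-Up Session in section 9.2. It starts from "prior PP studies in medical populations yielding a 64-85% completion rate of the exercises", concludes that "we will expect participants to complete at least 5 PP exercises", and then restates this in the other unit: "if a participant completes at least 5 sessions, missed sessions will not be considered a deviation from the protocol". The same sentence that sets the expectation of 5 gives the feasibility interest as patients' willingness to take part in the calls.

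For analysis, section 11.1 says that "descriptive statistics will be used to report proportion of phone session completion", together with mean exercise ratings.

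**The concern.** The exercises are homework: a gratitude letter, a new use of a personal strength during the week, a set of chosen activities. A call can go ahead with the homework undone, and nothing in the plan says that such a call does not count. The primary result could then say that the exercises are feasible when the number actually done was never measured.

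This is the primary endpoint, and the trial exists to refine the intervention before a larger pilot. If calls are well attended but exercises are often skipped, the exercises need changing. If exercises are done but calls are missed, the delivery does. A session count alone cannot tell these apart.

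**Working it through.** **1. The plan's threshold.** Take the 64-85% in section 9.2 (Follow-Up Session) as the share of assigned exercises completed. Of 8 exercises this gives:

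- 0.64 × 8 = 5.12
- 0.85 × 8 = 6.8

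The lower end, rounded down, is 5, and 5/8 = 62.5%. So the threshold is reproduced from the exercise rate. Sections 1.2 and 1.3 apply the same 5 of 8 to phone sessions.

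**2. The unit used at each place.**

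| Place | Unit |
|---|---|
| 1.2, Aim 1 | sessions |
| 1.3, Hypothesis 1, conclusion | exercises |
| 1.3, Hypothesis 1, rule | sessions |
| 9.2, Follow-Up Session, prior rate and expectation of 5 | exercises |
| 9.2, Follow-Up Session, deviation rule | sessions |
| 11.1, completion analysis | sessions |

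No place plans a count of exercises done.

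**3. How far the two counts could differ.** The documents give no split between calls and exercises, so the inputs here are assumptions: s, the weekly chance that the call is held, and q, the chance that the exercise was done given that it was. Treat weeks as independent, with the same rates for all patients, and count an exercise only if its call was held. Then

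P(at least 5 of 8) = Σ (k = 5 to 8) C(8,k) p^k (1 − p)^(8−k),

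with p = s for sessions and p = s × q for exercises.

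| Count | p | Patients reaching 5 of 8 |
|---|---|---|
| Sessions, s = 0.85 | 0.85 | 97.9% |
| Exercises, q = 0.75 | 0.85 × 0.75 = 0.638 | 67.9% |
| Exercises, q = 0.64 | 0.85 × 0.64 = 0.544 | 46.3% |
| Either, if q = 1 | 0.85 | 97.9% |

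In the third row the session rule passes and an exercise rule would fail.

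**4. Where the majority result turns.** Setting the sum to 0.5 gives p of about 0.56.

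**5. Against the protocol's own range.** In the failing row, 64% is a rate given that the call was held, so the overall rate is 54%. If 64-85% is instead the overall weekly exercise rate, the same formula gives 68.5% (p = 0.64) to 97.9% (p = 0.85) of patients reaching 5 of 8, a majority throughout.

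**The case against.** The strongest reply is that the protocol treats exercise and call as one unit. Every call opens with a review of the week's exercise, ratings follow the exercise and the call together, and the Follow-Up Session text passes from 5 exercises to 5 sessions as if they were equivalent. If the team counts a session only when the exercise was done, the gap closes. This stands in part. A reader might infer that a patient with five calls and no exercises is certain to count as a success. The documents do not go that far, because a completed session is undefined. They leave it open, and a review can equally find that nothing was done.

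A reader might also infer that the results will be judged against the prior 64-85%. No such comparison is planned. The range supports the expectation of 5 exercises and the deviation rule, and its link to Hypothesis 1 is the shared threshold of 5 of 8.

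It is also fair to say that the exercises are not ignored: their ease and utility ratings are part of Hypothesis 1. But section 9.2 has patients rate exercise and session jointly, and section 11.1 plans only mean scores, which do not show how many exercises were done.

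Finally, the intervention is phone-based, and the stated interest is willingness to take part in the calls. Counting sessions answers that question. This stands, and it argues against replacing the primary criterion with a stricter one that requires both call and exercise. It does not support a conclusion about the exercises drawn from calls alone.

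**Conclusion.** The point holds in a limited form. The plan as written can support a statement that the exercises are feasible without any measure of how many were done, and its threshold was set in one unit and applied in another.

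The size is uncertain. In the illustration, 97.9% of patients pass by sessions and 67.9% or 46.3% by exercises. This rests on assumed rates, independent weeks and equal rates across patients. With every exercise done, the two counts agree.

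It would be tempting to conclude that the feasibility result is likely to be wrong. The documents do not support that. Under this model the majority result reverses only when the overall weekly exercise rate is below about 0.56, and the protocol's prior studies lie at 64-85%. What is established is that the plan would not detect a reversal if one occurred.

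**What to change.** Keep 5 of 8 phone sessions by a majority of patients, and word it in section 1.3 as the criterion for feasibility of the phone-delivered intervention. State what makes a session completed.

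In section 9.2, have the interventionist record exercise done, yes or no, at the review step already in each call. In sections 1.3 and 11.1, report by week and per patient the calls held and the exercises done, and give the proportion of patients with at least 5 of 8 exercises done. Base any statement that the exercises are feasible on that proportion.

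The cost is one REDCap field per call and a few sentences of text. This version is dated 8/9/2019, after the estimated June 2019 completion in section 7.1, so some sessions may already have been held. For those, the field would have to be filled from session notes or ratings, where these allow it. The exercise figure may also come out lower than the session figure.

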After completion of the questionnaires, participants will be provided with a treatment manual, with weekly PP exercises for 8-sessions. All participants will be asked to complete 8 weekly PP exercises and will be asked to speak with the study interventionist, in this case the principal investigator, weekly. Immediately after the completion of the exercises, the participants will rate the ease of exercise completion, overall utility of the exercise, and their current levels of positive affect. For the last week of the intervention, baseline self-assessment questionnaires will be reviewed. At study completion, we will inquire about participants' potential interest in being contacted about our future studies. We will adhere to any and all participant requests regarding contact.

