**13.0 Withdrawal of Subjects\***

We do not anticipate any circumstances under which the subjects will be withdrawn from the research without their consent. We do not anticipate any termination of patients. When informed consent is being obtained from patients, we will emphasize to patients that they can withdraw from the study at any time for any discomforts. Subjects who withdraw from the study will still have their data potentially analyzed depending on when in the study they withdraw and patients will be informed of this as well. We will ensure that contact with participants is confidential by using only the phone numbers and other contact information that are specifically allowed by the participants and not leaving study-related messages for participants unless expressly allowed by participants. Upon enrollment, we ask all participants if it is acceptable to leave voice messages on their phones, as well as the appropriate times to call them. We adhere to any and all patient requests regarding contact.

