## **15.0 Potential Benefits to Subjects\***

Patients may not benefit from participating in this study. However, as part of the intervention, patients may obtain benefit from sharing their experiences especially as they explore and notice their positive experiences more than baseline. Contact with study interventionist and principal investigator may also provide support and social connection for study participants during the high risk post-discharge period of HSCT recovery.

Patients will be given the opportunity to identify positive emotions and consider ways to enhance their own positive emotions. Description of the PP exercises may enlighten them as to potential means of improving their own emotional states. Furthermore, they will have the opportunity to consider possible barriers to adherence to health-related behaviors. Patients who are identified as suffering from depression on the HADS scale will be offered opportunities to get treatment for such symptoms.

Optimism and other positive affective states are prospectively associated with increased participation in healthy behaviors in other medically ill populations and HSCT patients may benefit from this as well. This study therefore has the potential to identify key factors related to overall function, quality of life and adherence to health behaviors in HSCT patients. The creation of a PP-based intervention—based on this qualitative research phase—targeted at improving positive emotional states in HSCT patients could lead to a novel approach to enhancing adherence, overall function and quality of life in this population, which in turn might result in decreased morbidity and mortality in this population. Future studies could investigate the feasibility of implementing this

**PROTOCOL TITLE: Development of a positive psychology intervention to improve mood and health related quality of life in patients post hematopoietic stem cell transplantation- Proof of Concept Trial**

intervention in a similar population and examine the impact on psychological outcomes. If the PP intervention in these studies prove to be feasible, well-accepted, and associated with improvements in physical activity and other key outcomes, it may well be possible to utilize these easily-delivered and completed exercises as part of a clinical care package for HSCT patients. Thus participation in this study may result in substantial benefit to future patients.

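### Does the 6-out-of-10 acceptability criterion need a redefined rating and a rule that ease and utility must each reach 6?

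*Combined protocol and SAP*

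**What the plan says.** Acceptability is part of the primary aim (section 1.2) and of the primary endpoint (section 8.0). Its only numerical definition is in section 1.3: a "mean score of at least 6 out of 10 on ratings of ease of completion and subjective utility of the exercises".

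The rating is described twice:

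- Section 9.1 (Study Design): "Immediately after the completion of the exercises, the participants will rate the ease of exercise completion, overall utility of the exercise". No scale is named.
- Section 9.2 (weekly phone sessions): after both the exercise and the call, "participants will rate the ease of exercise/session completion, overall utility of the exercise/phone session", on 10-point Likert scales. The call itself contains "a review of the ease and utility of the week's PP exercise".

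Section 11.1 plans descriptive statistics for the "proportion of phone session completion and mean scores on exercise ratings". Section 13.0 covers those who leave: "Subjects who withdraw from the study will still have their data potentially analyzed depending on when in the study they withdraw". Sections 11.2 and 23.0 expect 25 enrolled and 10 completers.

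**The concern.** Three things look open in a primary criterion.

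1. **What is rated, and when.** Section 9.1 names the exercise. Section 9.2 joins exercise and call with a slash and places the rating after the call. The participant does the exercise alone, whereas the call is about 30 minutes with the interventionist. Section 15.0 adds that "Contact with study interventionist and principal investigator may also provide support and social connection for study participants". A score meant for the exercise could therefore reflect how the call was received.
2. **One threshold, two scales.** If ease and utility are averaged, a programme that is easy but not very useful could pass. Observed means of 7.5 and 5.0 average 6.25, which meets a combined rule and fails an each-scale rule.
3. **Averaging unit.** With heavy drop-out expected, the mean over all ratings and the mean over participants could differ, and the use of data from those who withdraw is left partly open.

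At stake is whether the acceptability statement carried into the larger pilot study could depend on a choice made after the ratings are seen.

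**Working it through.** The plan gives no expected ratings, SDs or error rates for this criterion, so there is no stated figure to reproduce. The check is a comparison of the text, followed by arithmetic on assumed values.

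**Step 1. Sections 9.1 and 9.2 side by side.**

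| | 9.1 | 9.2 |
|---|---|---|
| Role | design overview | procedure |
| Object | exercise | exercise/session, exercise/phone session |
| Timing | after the exercises | after exercise and call |
| Scale | none | 10-point Likert |
| Mood items alongside | positive affect | happiness and optimism |

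The last row shows 9.1 shortening what 9.2 spells out. Section 9.1 does not say that the rating precedes the call, so a rating taken as in 9.2 also satisfies 9.1. Section 1.3 itself judges the feasibility of the exercises by phone sessions completed. The Follow-Up Session text does the same: it expects at least five exercises and restates this as "if a participant completes at least 5 sessions". Exercise and session are one unit throughout. Sections 1.1, 1.2 and 8.0 make the intervention, which is delivered by phone, the object of acceptability.

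**Step 2. Each scale or combined.** Section 1.3 refers to ratings, in the plural, of two named attributes, and 11.1 to mean scores, also plural. The direct reading is one mean for ease and one for utility, each compared with 6.

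To size the alternative, assume one ease and one utility score per rater, n = 10 (sections 11.2 and 23.0), SD 2 and correlation 0.5. Section 9.2 in fact collects up to eight of each.

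- SE per scale = 2/√10 = 0.632.
- SE of the combined mean = 0.632 × √((1 + 0.5)/2) = 0.548.
- Combined rule: Φ((average of the two true means − 6)/0.548).
- Each-scale rule: bivariate normal probability that both sample means are at least 6.

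| True ease / utility | Combined | Each scale |
|---|---|---|
| 7.0 / 5.5 | Φ(0.25/0.548) = 0.676 | z = (1.581, −0.791): 0.213 |
| 6.5 / 6.5 | Φ(0.5/0.548) = 0.819 | z = (0.791, 0.791): 0.667 |
| 7.5 / 7.5 | Φ(1.5/0.548) = 0.997 | 0.983 |

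Over n = 10 or 25, SD 1.5 to 2.5 and correlation 0.3 to 0.7, the 7.0/5.5 case gives 63–85% (combined) against 5–26% (each). The 6.5/6.5 case gives 75–98% against 58–92%. The widest gap arises when the true means lie on opposite sides of 6. That is also the case in which two separately reported means show the problem at once.

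**Step 3. The slash item.** With assumed values of 5.5 for the exercise and 8 for the call, an equal blend is (5.5 + 8)/2 = 6.75, and a weight on the call of (6 − 5.5)/(8 − 5.5) = 0.20 is enough to reach 6. With 6.5 and 5, the blend is 5.75. The shift can go either way, and is nil for the verdict if both values lie on the same side of 6.

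**Step 4. Averaging unit.** Suppose 10 completers give eight ratings of 7, and 10 early leavers give two ratings of 4. Pooled mean: (10×8×7 + 10×2×4)/100 = 6.40. Participant-level mean: (10×7 + 10×4)/20 = 5.50. With leavers at 5 the two are 6.60 and 6.00, and both pass. Section 11.1 reads plainly as the mean of the ratings given. With only 10 of 25 completing (40%), the majority criterion (13) and the 80% follow-up criterion (20) in 1.3 would probably fail anyway.

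**The case for a change.** The best case for a change is that section 1.3 states a pass mark, and a pass mark loses value if its scoring rule is settled after the data are in. Participants must be shown one item, and the documents word it in two ways. Section 9.2, the only place with a scale, is likely to be the one used, while 1.3 and 11.1 speak of exercises. The interventionist is also the principal investigator, so a rating given just after discussing ease and utility on the call might be kinder than one given alone. A few sentences would settle all of this.

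Part of this stands. No sentence says outright that each scale must reach 6, and the wording of 9.1 and 9.2 differs. Those are omissions of detail. The argument that the call contaminates the rating does not stand: section 15.0 lists possible benefits of taking part and says nothing about ratings, and the call is part of the intervention whose acceptability is sought. Rating only the exercise, before the call, and keeping any call item out of the criterion would measure something narrower than the stated aim. That is a trade-off, with no clear gain.

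**Conclusion.** The concern does not call for a change. Followed as written, the plan yields mean ease and mean utility from the weekly ratings described in 9.2, each set against 6, and a utility mean below 6 would be visible beside a high ease mean. What is missing is a definition that an analyst would supply in the same sense.

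The size of the ambiguity runs from about 46 percentage points (67.6 − 21.3, true means 7.0 and 5.5) down to 1.4 points (99.7 − 98.3, both at 7.5). Every mean, SD and correlation behind those figures is assumed. The large figure also requires a combined mean to be scored alone, which the plural wording does not suggest.

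The consequence is limited as well. The study is a single-arm, unpowered proof of concept that reports acceptability descriptively, participants are also asked at follow-up what could be improved, and no section makes 6 out of 10 a binding condition for the next study. The conclusion would be different if the protocol tied a go/no-go decision to one combined score.
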